### **10.3 Clinical laboratory evaluations**

Testing for hepatitis B surface antigen and antibodies to hepatitis C and HIV will be performed at Screening. HLA-B27 will be performed at Screening only. These data will be listed only.

Descriptive statistics for observed values and change from Part A Baseline will be presented for each scheduled visit for the following parameters:

- Hematology: red blood cells, hemoglobin, hematocrit, platelets, white blood cells, neutrophils, lymphocytes, monocytes, eosinophils, and basophils
- Biochemistry: sodium, potassium, chloride, bicarbonate, total calcium, inorganic phosphorus, creatine phosphokinase (CPK), glucose, creatinine, urate, urea nitrogen, total protein, albumin, alkaline phosphatase (AP), aspartate aminotransferase (AST), alanine aminotransferase (ALT), bilirubin, total cholesterol

Values reported BLQ will be replaced by one-half the limit of quantification when reporting summary statistics.

Summaries for Part A will be presented by axSpA subpopulation and overall in the SS.

Summaries for Part B will be presented by treatment group in the SSB excluding any post-flare assessments in the subset of subjects experiencing a flare in Part B and start escape therapy. For the subset of subjects experiencing a flare in Part B and start escape therapy, separate summaries will be produced using the ETS and will present only the post-flare assessments by treatment group.

For the continuous laboratory parameters, last value (end of treatment), minimum value during treatment, and maximum value during treatment, will be derived. Derivations will be performed for each treatment period separately. The derivations will only use post-baseline assessments in the corresponding treatment period and will exclude any assessment performed at the SFU visit. In Part B, derivations will be done excluding all assessments performed after the start of escape therapy in subjects experiencing a flare in Part B and start escape therapy. Additional derivations will be performed for the subset of subjects experiencing a flare in Part B and start escape therapy using the ETS and including only the assessments performed after the start of escape therapy.

The calculations for end of treatment, minimum and maximum values will be performed for each parameter separately.

A by-subject listing of all laboratory data will be provided. This listing will be presented by treatment group, results (with abnormal values flagged) and unit. In the listing for biochemistry also Glomerular Filtration Rate will be added.

All laboratory values, for which a normal range is available, will be classified into low (L) normal (N), and high (H) according to the respective normal range. Values falling outside of the normal limits will be classified as H or L and values within the range with N. In case no lower (upper) limit is given, the classification L (H) is not applicable.

A summary of shift from Baseline to the maximum, minimum and end of treatment value will be provided for hematology and biochemistry parameters for each treatment period separately (Part A, Part B pre-flare, Part B post-flare).

Presentations in Part A will be performed by axSpA subpopulation and overall in the SS. Presentations in Part B pre-flare will be performed by treatment group in the SSB. Presentations in Part B post-flare data will be performed by treatment group in the ETS.

Markedly abnormal values at each post-Baseline visit will be defined as laboratory values graded 3 or 4 according to the Rheumatology Common Toxicity Criteria (RCTC). Values fulfilling the criteria will be classified as marked abnormal high (MH) or marked abnormal low (ML). In case no lower (upper) limit is given the classification ML (MH) is not applicable.

Definitions of markedly abnormal values are given in the below [Table 10.1](#) and [Table 10.2](#).

**Table 10.1: Definitions of Markedly Abnormal Hematology Values**

Parameter (SI units)	Markedly Abnormal Definition	
	Low	High
Hemoglobin (g/L)	<Lower Limit of Normal AND decrease from Baseline>20	N/A a
Hemoglobin (g/L)	<80	N/A
Leukocytes (total x 1000)	<2.0	N/A
Lymphocytes (x 1000)	<0.5	N/A
Neutrophils (x 1000)	<1.0	N/A
Platelets (x 1000)	<50	N/A

a N/A=not applicable.

**Table 10.2: Definitions of Markedly Abnormal Biochemistry Values**

Parameter (SI units)	Markedly Abnormal Definition	
	Low	High
AP	N/A a	>3 x ULN
ALT	N/A	>3 x ULN
AST	N/A	>3 x ULN
Calcium (mmol/L)	<1.75	>3.125
CPK	N/A	>4 x ULN
Creatinine	N/A	>1.8 x ULN
Glucose (mmol/L)	<2.22	>13.89
Potassium (mmol/L)	<3.0	>6.4
Sodium (mmol/L)	<125	N/A
Total bilirubin	N/A	≥2 x ULN
Uric acid	N/A	≥3 x ULN

a N/A=not applicable, ALT=alanine aminotransferase, AP=alkaline phosphatase, AST=aspartate aminotransferase, CPK=creatinine phosphokinase.

The number and percentage of subjects with markedly abnormal hematology or biochemistry values will be summarized by visit and for any visit (excluding the SFU visit) separately for each treatment period. Subject numbers for subjects with any markedly abnormal hematology or biochemistry value will be tabulated.

Summaries for Part A will be presented by axSpA subpopulation and overall in the SS. Summaries for Part B will be presented by treatment group in the SSB excluding any post-flare assessments in the subset of subjects experiencing a flare in Part B and start escape therapy. For the subset of subjects experiencing a flare in Part B and start escape therapy, separate summaries will be produced using the ETS and will present only the post-flare assessments by treatment group.

For the derivation of the number and percentage of subjects with markedly abnormal hematology or biochemistry at any visit within a treatment period, only post-baseline assessments within the corresponding treatment period will be considered (excluding the SFU visit). In Part B, derivations will be done excluding all assessments performed after the start of escape therapy in subjects experiencing a flare in Part B and start escape therapy. In the subset of subjects experiencing a flare in Part B and start escape therapy, derivations will be done including only the assessments performed after the start of escape therapy.

A by-subject listing of markedly abnormal values will be provided separately.

The number and percentage of post-baseline liver function test evaluations will be summarized by varied ULN parameter criteria for ALT, AP, AST and total bilirubin separately for each treatment period, using same derivation as described previously. Presentations in Part A will be performed by axSpA subpopulation and overall using the SS. Presentations in Part B will be performed by treatment group using the SSB. For the subset of subjects experiencing a flare in Part B and do start escape therapy, presentations will be performed by treatment group using the ETS.

The varied parameter criteria will be:

- $\geq 2x$ , 3x, 5x, 10x, 20x ULN elevation of AST
- $\geq 2x$ , 3x, 5x, 10x, 20x ULN elevation of ALT
- $\geq 2x$ , 3x, 5x, 10x, 20x ULN elevation of AST or ALT
- $\geq 1x$ , 1.5x ULN elevation of Bilirubin
- $\geq 1.5x$  ULN elevation of AP
- $\geq 2x$  ULN elevation of Bilirubin and 3x ULN elevation of either ALT or AST

In order to meet the last above criteria, a subject must experience the elevation in bilirubin and ALT or AST at the same visit. For example, a subject who experiences a  $\geq 2x$  ULN elevation of bilirubin at one visit and a 3x ULN elevation in ALT (or AST) at a subsequent visit has not fulfilled the Hy's law criteria.

A by-subject listing for any subject with at least one post-baseline elevated test data will be provided. The listing includes all liver function test laboratory values for this subject.

Samples and results for additional laboratory tests (hepatitis B surface antigen and antibodies to hepatitis C and HIV, Genomics Laboratory Data, HLA-B27) will be listed separately.

The urinalysis data will be listed only.

## **10.4 Vital signs, physical findings, and other observations related to safety**

### **10.4.1 Vital signs**

Vital signs, including temperature, will be measured at all on-site visits (except at the 3 to 5 days prior to Week 48 Visit) including the SFU visit and also at all home-nurse visits in Part B. In subjects experiencing a flare in Part B, vital signs will be measured at escape Weeks 0, 2, 4, 12 and every 12 weeks thereafter. Respiration rate will be measured at Screening and Baseline only; and in addition at subsequent visits, if a subject experiences an AE.

Descriptive statistics for observed values and change from Part A Baseline will be presented for each scheduled visit for each vital sign parameter.

Vital signs will be presented for Part A and Part B separately. Part A summaries will be done by axSpA subpopulation and overall using the SS. Part B summaries will be done by treatment group using the SSB. Part B summaries will not include post-flare assessments. For the subset of subjects experiencing a flare in Part B and start escape therapy, summaries will be produced using the ETS including only the post-flare assessments. Vital signs assessments will be listed.

### **10.4.2 Other safety variables**

The following presentations will be based on the SS for Part A and on the SSB for Part B, unless otherwise mentioned.

#### **10.4.2.1 Pregnancy testing**

Pregnancy testing must be carried out for women of childbearing potential and will consist of serum testing at Screening and SFU, and urine testing at Baseline and Week 96/withdrawal Visit. Pregnancy test results (i.e. Choriogonadotropin Beta) will be listed only.

#### **10.4.2.2 Physical assessments**

Physical examination will be performed at Screening, Baseline, Weeks 12, 24, 36, 48, 60, 72, 84, 96/withdrawal, and at the SFU visit (10 weeks after the last dose). In subjects experiencing a flare in Part B, physical examination will be performed at escape Weeks 0, 2, 4, 12 and every 12 weeks thereafter. Clinically important abnormal changes in subsequent physical examinations will be recorded as AEs. Physical examination results will be listed.

Weight is to be measured at Screening, Baseline, Week 48, and at completion at Week 96/withdrawal Visit. Height will be measured at the Baseline Visit only. Summary statistics will be provided by axSpA subpopulation and overall in Part A using the SS and by treatment group in Part B using the SSB by visit presenting actual values and changes from Part A Baseline for weight, height and BMI, as applicable. The summary for Part B will not include post-flare assessments. For the subset of subjects experiencing a flare in Part B and start escape therapy, a summary by treatment group will be produced using the ETS including the post-flare assessments. These data will also be listed.

#### **10.4.2.3      Tuberculosis assessments**

During the conduct of the study, the tuberculosis (TB) assessment by IGRA (QuantiFERON TB GOLD In Tube test or Elispot, if QuantiFERON TB GOLD In Tube test is not available locally), will be repeated at Week 48 and Week 96/withdrawal Visit for all subjects.

Tuberculosis testing results will be listed.

A plain posteroanterior chest x-ray (or, if done, computed axial tomography of the chest) must be done within 3 months prior to the Screening Visit. The chest x-ray should be repeated only if the TB test was confirmed positive or any further evidence is suggestive of potential TB infection (eg, exposure).

Chest x-ray results will be listed.

REDACTED COPY  
This document cannot be used to support any marketing authorization application and any extensions or variations thereof.

## 12 APPENDICES

### 12.1 Rules for medical resource utilization

#### 12.1.1 Healthcare Resource Utilization

Study-specific modules will be used to capture the following data regarding healthcare resource utilization during the study:

- Concomitant medical procedures
- Health care provider consultations not foreseen by the protocol
- In-patient hospitalizations and emergency room visits (including length of stay)

In addition to the above categories, the duration of hospital stay will be calculated.

#### 12.1.2 Counting rules

##### 12.1.2.1 In-patient hospitalization and emergency room visits

1. In case of complete admission and discharge dates, for the same subject only one hospitalization will be considered if “start date of the second hospitalization - end date of the first hospitalization  $\leq 1$ ”.
2. In case the discharge date for a hospitalization is missing (regardless of the discharge check value),
  - if there is a subsequent hospitalization,
    - if the initial entry point and relationship are the same between the 2 hospitalizations, then the first hospitalization will be grouped with the next one
      - (1) if the discharge date of the second hospitalization is non-missing, then length = second hospitalization discharge date – first hospitalization admission date +1;
      - (2) else,length = last non missing visit date – first hospitalization admission date +1 .
    - otherwise, if either the entry point or the relationship of the 2 hospitalizations is different, then both hospitalizations will be counted as distinct. In this case the length of the first hospitalization will be computed as follows:  
length = (second hospitalization admission date – 1) – first hospitalization admission date + 1= second hospitalization admission date – first hospitalization admission date.
  - in case there is no subsequent hospitalization, then the length of the hospitalization is calculated as

$$\text{length} = \text{last non missing visit date} - \text{hospitalization admission date} + 1.$$

---

3. In case the last visit date is before the start date, then the discharge date for a hospitalization is replaced by the start date of hospitalization and the length of the hospitalization is equal to 1.

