### **8.3.1.23 Resources utilization**

Summary statistics and frequency distribution (number of subjects by number of medical resources used) will be presented by axSpA subpopulation and all subjects for concomitant medical procedures, health care provider consultations, and in-patient hospitalizations and emergency room visits, including length of stay. These summaries will be produced for the OLS using observed case data.

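### The rule for missing discharge dates can impute a hospital stay of many months and merge separate admissions, because it ignores the study visits attended in between

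*SAP*

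**What the plan says.** SAP Section 12.1.2.1 gives three counting rules for in-patient stays.

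- **Rule 1** covers complete dates. Two admissions of one subject count as one if the second starts at most 1 day after the first ends.
- **Rule 2** is triggered "In case the discharge date for a hospitalization is missing (regardless of the discharge check value"). It has three branches:
  - A later admission with the same entry point and relationship: "then the first hospitalization will be grouped with the next one". If the second discharge date is known, "then length = second hospitalization discharge date – first hospitalization admission date +1". If it is missing too, "else,length = last non missing visit date – first hospitalization admission date +1".
  - A later admission with a different entry point or relationship: "then both hospitalizations will be counted as distinct", and the first stay ends the day before the second admission.
  - No later admission: "in case there is no subsequent hospitalization, then the length of the hospitalization is calculated as" the last non-missing visit date minus the admission date plus 1.
- **Rule 3** begins "In case the last visit date is before the start date" and sets the length to 1 day in that case.

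Section 3.2.17 assigns each resource item to Part A, Part B or post-flare by its start date. Section 8.3.1.23 asks, for Part A, for summary statistics and frequency distributions of "in-patient hospitalizations and emergency room visits, including length of stay".

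**The concern.** A missing discharge date does not mean that the subject stayed in hospital. The trial holds other evidence on this: subjects come to study visits, and visit dates are recorded and listed (Section 5.1). Rule 2 uses only the last of these visits, or the next admission, and passes over every visit before that. A subject can therefore be counted as an in-patient through a long run of attended on-site visits.

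Nothing bounds the result from above. Rule 3 applies only when the last visit precedes the admission, so it never shortens a long stay. The merging branch sets no limit on the gap between the two admissions. Section 3.2.17 fixes the study part by start date, but no text cuts the length at the end of that part.

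At stake are the mean and maximum length of stay, which a single incomplete record can dominate, and the number of admissions, which falls by one for each unjustified merge.

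**Working it through.** **The plan's own arithmetic.** For two distinct admissions the SAP simplifies (second admission − 1) − first admission + 1 to second admission − first admission. With days 100 and 170, both sides give 70, so the identity holds.

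**Latest regular visit.** Section 2.3.4 puts the last double-blind dose at Week 94 and the safety follow-up (SFU) visit 10 weeks after the last dose. 94 + 10 = Week 104, or day 104 × 7 = 728. This agrees with the stated duration: 5 + 48 + 48 + 10 − 2 = 109 weeks, less 5 weeks of screening = 104.

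**Assumed inputs.** The SAP gives no admission dates or typical lengths. The admission weeks and the 5-day stays below are illustrations. The SFU visit is taken as the last non-missing visit, which the SAP does not state.

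**No later admission.** Length = last visit − admission + 1.

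- Admitted Week 12 (day 84), last visit Week 104: 728 − 84 + 1 = 645 days.
- Admitted Week 24 (day 168), last visit Week 104: 728 − 168 + 1 = 561 days.
- Admitted Week 90 (day 630), last visit Week 104: 728 − 630 + 1 = 99 days.
- Subject leaving after Part A, admitted Week 24, last visit Week 56 (assumed last dose at Week 46, plus 10 weeks; day 392): 392 − 168 + 1 = 225 days.

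In the first case the stay is tabulated in Part A, where only 48 − 12 = 36 weeks, or 252 days, remained at admission.

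**Later admission, same entry point and relationship.** First admission Week 12 (day 84), second at Week 60 for 5 days (days 420 to 424): 424 − 84 + 1 = 341 days, counted as one hospitalization. This pair spans Parts A and B, and the SAP does not say whether a subsequent hospitalization may lie in another part. With both admissions in Part A, the second at Week 40 (days 280 to 284), the merged stay is 284 − 84 + 1 = 201 days.

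**Later admission, different entry point or relationship.** Weeks 12 and 60 again: the first stay is 420 − 84 = 336 days.

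**Effect of one 645-day record on the mean**, for assumed numbers of stays:

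| Other stays last | 50 stays | 20 stays |
|---|---|---|
| 3 days | (49 × 3 + 645)/50 = 15.8 | (19 × 3 + 645)/20 = 35.1 |
| 5 days | (49 × 5 + 645)/50 = 17.8 | (19 × 5 + 645)/20 = 37.0 |
| 10 days | (49 × 10 + 645)/50 = 22.7 | (19 × 10 + 645)/20 = 41.8 |

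**With the cap proposed under the fix.** After Week 12 the next Part A time point listed in Section 3.3 is Week 24 (day 168). If that visit was attended on site, the stay ends at the latest on day 167: 167 − 84 + 1 = 84 days instead of 645.

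**The case against.** Much can be said on the other side.

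- **Conflict with rule 1.** A reader might infer that merging at any gap contradicts the 1-day limit. It does not. Rule 1 is confined to complete dates and rule 2 to missing discharge dates. Section 3.2.17 repeats the 1-day rule without that condition, but the gap cannot be computed without the first end date. The two rules follow different principles without contradicting each other.
- **Reach.** A reader might infer that length of stay is reported in all study parts and so bears on the randomized comparison. Among the analysis sections only 8.3.1.23 names it, and Part A is open-label with one treatment. Sections 8.3.2.12 and 8.3.3 list hospitalizations and emergency room visits for Part B and post-flare without it. Sections 3.2.17 and 12.1.1 say only that it is collected and calculated.
- **Discharge check.** A reader might infer that the rule overrides a recorded discharge. That is the natural reading, but the SAP never defines the check. The point does not need it, because the attended visits suffice.
- **Size.** Neither the number of hospitalizations nor the number of missing discharge dates is given. Section 3.1 also requires the median, minimum and maximum, so one extreme value would be visible and would barely move the median.

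All four stand as limits on the point. None removes it: the stated rule still yields lengths that attended visits show to be implausible, and it can still reduce the count of admissions.

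**Conclusion.** The point holds in a limited form. Followed as written, rule 2 can impute stays of many months (645 and 341 days in the illustrations) and can count two separate admissions as one. The long lengths assume that the SFU visit is the last visit. The 341-day case also assumes that merging may cross study parts.

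The damage is confined to descriptive resource-use summaries, which are an other efficacy variable: length of stay as named for Part A, and the number of admissions. No hypothesis test, model, or primary, secondary or safety analysis uses them. How often this will happen cannot be judged from the SAP. The correction is still worth making, because it is cheap and uses data already collected.

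**What to change.** Amend rule 2 of Section 12.1.2.1 as follows.

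1. In all branches, an imputed stay ends no later than the day before the first on-site study visit attended after the admission date.
2. Two admissions are grouped only if no on-site study visit was attended between them. Otherwise they are counted separately, with the first stay capped as in item 1.
3. Where no on-site visit intervenes, the existing rule stands. Rule 3 is kept.

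The cost is a few lines of SAP text and a small programming change to bring in the visit dates. The capped length is still an upper bound, on the premise that a subject who attends an on-site visit has left hospital. In Part A, where the listed time points can lie 12 weeks apart, that bound can still be as long as 84 days.

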#### **12.1.2.2 Healthcare provider consultations not foreseen by the protocol**

In case of complete consultation date, count only once for the same subject, same consultation date, same location, and same provider.

#### **12.1.2.3 Concomitant medical procedures**

If the procedure name, start date, and relationship are the same, then only 1 procedure is counted, otherwise if at least 1 variable among procedure name, start date, or relationship is different, distinct/several procedures are counted.

### **12.2 Compliance ratio calculation**

The general formula for treatment compliance is given as follows:

$$\text{Compliance Ratio (CR)} = \{[\text{Exposure Duration (days)}] - [\text{Cumulative Difference (days)}]\} / \{\text{Exposure Duration (days)}\}$$

There are 2 methods to determine the CR. CR(1) is based upon scheduled days which reference the Baseline Visits. CR(2) is based upon scheduled days which reference the previous dosing administration date. CR(1) and CR(2) each will be computed separately. The definition of exposure duration and cumulative difference varies for the 2 calculations. In all cases, if the subject was randomized, but study drug was never administered then the CR is equal to 0. The CR is limited to a range of 0 to 1. Therefore, if for any reason a negative value is computed, the CR must be set to 0. Specific details for each calculation follow.

#### **CR(1):**

$$\text{Exposure Duration (days)} = \text{Last Visit date} - \text{Baseline date} + 14$$

$$\text{Cumulative Difference (days)} = \sum_i \text{ABS}(\text{AD}_i - \text{SD}_i), \quad \text{where } i = \text{Week 0, 2, 4, 6, } \dots, \text{XX}$$

where  $\text{AD}_i = \text{Actual day of administration, for Week } i=0 \text{ to XX by 2}$   
 $\text{SD}_i = (i/2) \times 14, \quad \text{for Week } i=0 \text{ to XX by 2}$

**Note:** XX represents the last completed visit in which study drug should have been administered. If subject is still in the study but  $\text{AD}_i$  is missing, then  $\text{ABS}[\text{AD}_i - \text{SD}_i] = 14$  for the missed Visit i.

